5.1 Protection against risks

Potential Risks

The risks from this study are minimal, primarily consisting of mild hypernatremia. However, published data involving this population and at dose of sodium supplementation to be provided in this study have not shown any harmful effects, including hypernatremia, suggesting this risk is minimal [33, 43]. Additional risks relate to the collection of biological samples, and collection of clinical data with the potential for loss of confidentiality.

Adequacy of the Protection against Risk

Recruitment and Informed Consent

Neonatal research nurses/coordinators are a key element in the success of clinical research programs within neonatal intensive care units. The team of research coordinators will be in constant communication with the NICU care team to assist in identification of eligible patients. They will screen patients and present to the parents the details of the study and obtain informed consent. The experience of the research coordinators results in effective communication about protocols and success in recruitment. Based upon completion of a large number of studies in the NICUs, we anticipate approximately a 60% enrollment. The drop-out rate is likely to be minimal given the limited interventions and lack of anticipated side effects from the intervention.

Protecting Confidentiality

Security measures to protect subject identities include the use of coded files to unlink research records from names and other identifiers, locked storage areas, and password-protected computer files. Subjects' names are linked to their IDs as noted above. Access to computer systems housing sensitive information is strictly regulated. Credentials permitting access to these systems are granted only to essential investigators and research personnel. All systems are secured from external attack through a combination of hardware and software firewalls and are updated with necessary security patches as they become available. Related hardware and back-up storage media are maintained in a secure environment to which only essential personnel have physical access. All consent and research procedures will be compliant with Subpart B of the Code of Federal Regulations Title 45, Part 46 - Protection of Human Subjects with Additional Protections for Pregnant Women, Human Fetuses and Neonates Involved in Research (66 FR 56778, Nov. 13, 2001).

5.2.1 Data management and interpretation

Data will be collected using prepared forms, then entered and managed using REDCap electronic capture tools hosted and managed by IUPUI Biostatistics. The REDCap platform is a secure, webbased application designed to support data capture for research studies, providing: 1) an intuitive interface for validated data entry; 2) audit trails for tracking data manipulation and export procedures; 3) automated export procedures for seamless data downloads to common statistical packages and 4) procedures for importing data from external sources. Only IRB approved research team members will have access to the REDCap data platform. Each team's members will be granted access to the REDCap data system through a secure login. In the REDCap data platform, primary data and data backups are secured at separate Indiana University Data centers. Operating system security includes: secure logins, data encryption at rest, remote system logging and configuration and change management. Data backups are encrypted both in flight and at rest. Copies of data are replicated to the remote data center every 15 minutes. There are 100+ point-in-time copies of data available at any time. Disaster recovery has been tested and confirmed.

Performance Monitoring: Standard reports will be generated from the study database by the

Data Center. These will include monthly reports that provide the number of infants screened and enrolled, missing data, adherence to study protocols, and a variety of performance measures, including adverse events.

5.2.2 Statistical analysis

All analyses will be performed on an intent-to-treat basis. The primary analysis (and all analyses examining outcomes by treatment) will be adjusted for the stratification variable of gestational age. Since the primary outcome is continuous, linear regression will be used to estimate the adjusted mean difference in growth between the two treatment groups. Similarly, for secondary outcomes, linear regression will be used for continuous outcomes and robust Poisson regression for binary or categorical outcomes to obtain adjusted relative risk estimates for the treatment effect.

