3.2 DETAILED STUDY PROCEDURES

- All study events described below have a ±2 day range for execution.
- Doubly labeled water procedure will occur from corrected week 32 to corrected week 32 + 6 days
- Date of birth is considered day 0
- See Appendix for table of events

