3.2.3 Randomization Procedure

An infant must meet all inclusion criteria and no exclusion criteria at the time of randomization. After meeting eligibility and obtaining consent, randomization will be carried out in REDCap to management arms 1:1, using a permutated block scheme stratified by gestational age at birth: $25 \, \text{O}/7 - 27 \, \text{O}/7$ and $28 \, \text{O}/7 - 29 \, \text{O}/7$ weeks.

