3.2.8 Primary Outcome

The change in somatic growth (weight gain, head circumference, and length) evaluated by the change in Z-score between 2 weeks of age and 36 weeks conceptual age or transfer from NICU. Weights will be extracted from the medical record, consistent study personnel will obtain the length (using a length board) and OFC.

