5.2.3 Sample size and power estimates

Sample size and power calculations for this study are based upon the primary outcome of differences in weight gain between the two groups of infants. Using data from our recently completed analysis, in which infants 26 – 29 6/7 weeks gestation treated according to the algorithm were compared with historical controls, and based upon identifying a difference in weight Z-score of 0.25 at 36 weeks postmenstrual age, using a SD of 0.4 with an alpha = 0.05 and power of 0.8, we calculate we will need a total sample size of 82 patients (41 per group). With regards to the secondary outcome of EE, and based upon published data of EE estimated in preterm infants using the DLW method, a sample size of 41 patients per group will allow us to detect a 6% difference in EE, assuming an alpha = 0.05 and a power of 0.80. With regards to TBW, and based upon data from these same investigators who report a mean TBW of 80.8% body weight, with SD of 3.1%, this sample size will allow us to detect a difference in TBW of 2.0% between groups, assuming an alpha = 0.05 and a power of 0.80. To acknowledge for study drop out, we will plan to enroll up to 90 patients (plus 90 mothers for chart review).

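### The primary change-in-Z-score regression names only the gestational-age stratum as a covariate; adding the 2-week Z-score would buy a modest, nearly free gain in precision

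*Combined protocol and SAP*

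**What the plan says.** Section 3.2.8 defines the primary outcome, for weight, head circumference and length, as growth "evaluated by the change in Z-score between 2 weeks of age and 36 weeks conceptual age or transfer from NICU".

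Section 5.2.2 gives the model: "linear regression will be used to estimate the adjusted mean difference in growth between the two treatment groups". On covariates it says: "The primary analysis (and all analyses examining outcomes by treatment) will be adjusted for the stratification variable of gestational age". No other covariate is named.

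Section 3.2.3 shows what that variable is. Allocation is 1:1, "using a permutated block scheme stratified by gestational age at birth", with two strata (25–27 and 28–29 weeks).

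Section 3.2.5 lists possible confounders to be collected. It assigns none of them to a model, and the 2-week Z-score is not on the list.

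Section 5.2.3 sizes the trial on weight, by "identifying a difference in weight Z-score of 0.25 at 36 weeks postmenstrual age, using a SD of 0.4", with alpha 0.05 and power 0.80. This gives 41 per group, 82 in all, with enrolment of up to 90 to allow for drop-out.

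**The concern.** Analysing a change score without its baseline fixes the slope of the 36-week value on the 2-week value at exactly 1. If the true slope is below 1, two things follow:

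- Variation in the outcome that the 2-week value could explain stays in the residual.
- A fraction (1 − slope) of any chance difference between arms at 2 weeks stays in the estimated treatment effect.

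Stratifying on gestational age does not prevent such a difference, because a Z-score is already standardised for age. With about 41 infants per arm and no stratification on size, some imbalance is to be expected.

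What is at stake is efficiency, and how far the one estimate the trial reports depends on the luck of its allocation. Bias and type I error are not in question. The calculated sample size meets 0.80 power with no reserve beyond the drop-out allowance, so a gain from data already collected is worth having.

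**Working it through.** **Inputs from section 5.2.3.** Difference d = 0.25; SD 0.4; alpha 0.05; power 0.80; 41 per arm.

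**Assumptions, because the documents are silent.** The 0.4 is the SD of the change score. The Z-score SD, s, is the same at both ages and lies between 0.6 and 1.0. Alpha is two-sided.

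**1. The plan's own figure.** n per arm = 2 × (1.960 + 0.842)² × 0.4² / 0.25² = 40.2, rounded up to 41, so 82 in total. This matches the plan. A one-sided test would give 32 per arm, so two-sided alpha was used. By noncentral t, power at 41 per arm is 0.798. The standard error of the treatment effect is 0.4 × √(2/41) = 0.088, and the 95% CI half-width is 0.176.

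**2. Correlation implied by the assumptions.** With equal SDs, the variance of change is 2s²(1 − r), so r = 1 − 0.4²/(2s²). The slope then equals r.

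**3. Effect of adding the 2-week Z-score.** Residual variance is multiplied by (1 + r)/2. A one-standard-error imbalance at 2 weeks, s × √(2/41), moves the unadjusted estimate by (1 − r) × s × √(2/41).

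| s | r | Variance ratio | Power, 41 per arm | Shift from one-SE imbalance |
|---|---|---|---|---|
| 0.6 | 0.778 | 0.889 | 0.84 | 0.029 |
| 0.8 | 0.875 | 0.938 | 0.82 | 0.022 |
| 1.0 | 0.920 | 0.960 | 0.81 | 0.018 |

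Residual variance therefore falls by 4–11%, or about 3–10% after the cost of estimating the slope (about 1.3% of variance). The CI half-width goes from 0.176 to about 0.167–0.173. The shift is 7–12% of the 0.25 target, or 0.2–0.33 of the 0.088 standard error.

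**4. Simulation.** There were 20,000 trials for each s, with the stratum in both models. The mean estimate was 0.250–0.251 under both. Coverage was 94.6–94.9% without the 2-week value and 94.7–95.0% with it. Power was 0.80 without it, and 0.840, 0.818 and 0.806 with it. In a separate run with no true effect and r = 0.8, type I error was 0.049 without and 0.050 with.

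**5. Sensitivity to the equal-SD assumption.** Hold the SD of change at 0.4 and let s0 be the 2-week SD.

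- The slope equals 1, and the gain is nil, when the ratio of the 36-week to the 2-week SD is √(1 + (0.4/s0)²). That is 1.20, 1.12 and 1.08 for s0 = 0.6, 0.8 and 1.0.
- With a ratio of 1.05, the net variance gain after the slope cost is 5.4%, 0.9% and −0.8%, and power is about 0.82, 0.80 and 0.795.
- With a ratio of 0.9, the variance ratio before the slope cost is 0.774, 0.806 and 0.809, a gain of 19–23%.

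**The case against.** The strongest reply is that nothing here is an error. A pre-specified linear regression of a change score, adjusted for the stratification variable, is a complete and legitimate primary analysis, and the simulation confirms that it is unbiased with correct coverage. That stands, and the point is put as an improvement only.

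The second reply is that the size of the gain rests on undocumented inputs. This also stands. A 36-week SD only 5% above the 2-week SD removes nearly all the benefit in two of the three scenarios. Against that, the risk is lopsided. If the covariate explains nothing, the cost is about 1.3% of variance, or roughly half a power point (0.798 to 0.793); if the SD narrows by 36 weeks, the gain is several times larger.

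Third, lost precision and leftover imbalance are one quantity seen two ways: 0.33² is about 11% and 0.2² is 4%. That is correct, and the two should not be added together. The planned standard error already allows for such imbalance on average.

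Fourth, up to 90 infants may be enrolled and section 5.1 expects little drop-out. With all 45 per arm analysed, power would be 0.835 without the covariate. But 90 is a ceiling and a drop-out allowance, and the covariate would help at that size too.

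Finally, section 5.2.2 does not use the word only. The reading rests on no other covariate being named there or assigned to a model elsewhere.

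**Conclusion.** The point holds. The primary model names no covariate beyond the gestational-age stratum, and it omits the baseline from which the change is computed. The likely loss is modest: 4–11% of residual variance and about 1–4 power points at 41 per arm. This assumes an SD of change of 0.4 and equal Z-score SDs of 0.6–1.0 at the two ages. The gain could be nil or very slightly negative if the 36-week SD is somewhat larger, and about 19–23% of variance if it is 10% smaller. All these figures are for weight; the documents give no SD for length or head circumference. Confidence in the direction is good, and in the size only moderate. The analysis as planned remains valid, so this is a recommended refinement.

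**What to change.** In section 5.2.2, pre-specify the primary model as linear regression of the 36-week Z-score (or, equivalently for the treatment effect, the change) on arm, the 2-week Z-score of the same measure and the gestational-age stratum.

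Use as covariate the same 2-week measurement that defines the change, and state that it is the one taken before study supplementation starts. This needs saying because section 3.2 provides that "All study events described below have a ±2 day range for execution".

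For consistency, use the same form for weight, length and head circumference, and for the secondary growth outcome to discharge, transfer or 44 weeks. Entering gestational age in days or weeks is optional; no gain from it has been shown. Naming the covariate in advance also removes any later choice between adjusted and unadjusted results in an unmasked trial.

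The cost is one sentence in the plan and one degree of freedom per model, about 1.3% of variance at N = 82. No new data are needed. If change proves unrelated to the 2-week value, that small cost is not recovered.

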- Nutritional intake data: Parenteral intake of fluid, protein, lipid, calories and sodium will be recorded each Monday, Wednesday and Friday from day of life until 38 weeks postmenstrual age or hospital discharge. Enteral intake of milk/formula volume, sodium and calories will similarly be recorded each Monday, Wednesday and Friday. Sodium content of breast milk will be estimated at 0.8 mEq/100 ml. Milk fortified to 24 and 27 kcal/oz with human milk fortifier (HMF) will be estimated to have sodium content of 1.4 and 1.8 mEq/100 ml, respectively. Sodium content of formula will be as described by the manufacturer.
- Anthropomorphic measurements: Measurements will be obtained weekly until discharge/transfer or until 44 weeks corrected age (whichever occurs first). Weights will be

extracted from the medical record. Research staff will obtain the length (using a length board) and OFC.

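### Section 5.2.2 gives no method for infants without a final growth value, so they fall out of the primary analysis by default, although weekly measurements already collected could keep many of them in

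*Combined protocol and SAP*

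**What the plan says.** The primary outcome (section 3.2.8) is the change in Z-score for weight, length and head circumference between two time points: 2 weeks of age, and 36 weeks or transfer from the NICU. In section 5.2.2, "linear regression will be used to estimate the adjusted mean difference in growth between the two treatment groups", with adjustment for the gestational-age stratum. The same section states that "All analyses will be performed on an intent-to-treat basis".

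Growth is recorded far more often than the model uses it. Under section 3.2.5, "Measurements will be obtained weekly until discharge/transfer or until 44 weeks corrected age (whichever occurs first").

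Some loss is foreseen:
- Section 5.2.3: "To acknowledge for study drop out, we will plan to enroll up to 90 patients".
- Section 3.1.2 withdraws infants who receive an ostomy after entry.
- Section 5.3 tracks mortality through 36 weeks as a safety outcome.
- The Appendix has a Week 36 Status form that is also completed when an infant leaves the study early.

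No section gives a missing-data method, a rule for deaths or withdrawals in the growth analysis, or a sensitivity analysis. Missing data are mentioned only as an item in the monthly performance reports (section 5.2.1).

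**The concern.** A regression of a two-point change needs both points. With no rule for a missing second value, software omits the infant, and the analysis becomes one of infants with complete endpoints while carrying an intent-to-treat label. The routes to a missing value are withdrawal by parents or after an ostomy, early discontinuation, death and, on the literal wording, discharge home before 36 weeks (discharge is named in the secondary growth outcome but not in the primary). Ostomy and serious illness are plausibly related to growth, and caregivers and parents know the allocation (section 3.2.7), so loss could also differ between arms. If it does, the estimated treatment difference is biased, and enrolling more infants does not repair that. The weekly measurements show how a lost infant was growing before loss, and the stated model ignores them.

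**Working it through.** **1. The plan's sample size.** Section 5.2.3 gives the target as "identifying a difference in weight Z-score of 0.25 at 36 weeks postmenstrual age". The spread and error rates come from the same section: "using a SD of 0.4 with an alpha = 0.05 and power of 0.8". Allocation from section 3.2.3: "randomization will be carried out in REDCap to management arms 1:1". Sidedness is not stated, so two-sided is assumed (one-sided would give 32 per group).

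n per group = 2 × (1.960 + 0.842)² × 0.4² / 0.25² = 2 × 7.85 × 2.56 = 40.2, rounded up to 41. This matches "we calculate we will need a total sample size of 82 patients (41 per group"). Enrolling 90 allows for 8/90 = 8.9% loss; the plan states no rate.

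**2. Power after random loss.** With m analysed per arm, power = Φ(0.25 / (0.4√(2/m)) − 1.96). For m = 41 the standard error is 0.088 and power is Φ(2.83 − 1.96) = 0.808 (t test 0.798).

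| Lost from 90 | m per arm | Power (normal / t) |
|---|---|---|
| 8.9% | 41 | 0.808 / 0.798 |
| 15% | 38.25 | 0.780 / 0.770 |
| 20% | 36 | 0.755 / 0.744 |

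Random loss at the planned level costs little.

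**3. What the weekly data offer.** From 2 weeks of age to 36 weeks the window is 36 − 27 = 9 weeks for birth at 25 0/7, and 36 0/7 − 31 6/7 = about 4 weeks for birth at 29 6/7. That is about 10 and 5 weekly values; the primary model uses two.

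**4. Bias under growth-related loss.** These simulations are illustrative: true difference 0.25, SD of change 0.4, 90 infants, about 8 lost. The loss patterns and within-infant covariances are assumed. Where interim data were used, loss depended on growth already observed.

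| Assumed loss | Complete cases | Using interim values |
|---|---|---|
| Random | 0.248 | 0.249 |
| Slow growers, equal numbers lost per arm | 0.248–0.250 | not run |
| Slow growers, one rule for both arms, windows of 4 to 9 weeks | 0.21–0.22 | 0.25 |
| Growth-related in controls only, same overall rate in each arm | 0.219 | 0.253 |
| Slow growers, controls three times as readily, covariance known | 0.23 | 0.25 |
| Same, covariance estimated from the data | 0.21–0.22 | 0.25 |
| Same, windows of 4 to 9 weeks | 0.19–0.21 | 0.25 |
| Slow growers, 3:1 by arm, separate complete-case run | 0.21–0.24 | not run |

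The third row needs no difference in the loss rule. If the algorithm works, more controls are slow growers, so one rule removes more of them.

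A shift from 0.25 to 0.19–0.23 is 0.02 to 0.06, or 8% to 24% of the target (0.02/0.25 and 0.06/0.25). Against a standard error of 0.088 it is about 0.2 to 0.7 standard errors. Under random loss the interim data cost nothing: the empirical standard error is 0.087 against 0.089 at 8.9% loss, and 0.088 against 0.093 at 20%.

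**The case against.** The strongest reply has five parts.

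- *Drop-out may be small.* Section 5.1 expects it to be minimal, the infants are inpatients, and weights come from the medical record. This stands in part: with little loss the effect is small. But no rate is given, and nothing says that measurements continue after withdrawal.
- *The Week 36 Status form may supply an early leaver's endpoint.* It may, but no rule says so. In the simulation with growth-related loss in controls only, substituting the last value gave 0.242 against 0.219 for omission. It also gave 0.238 under purely random loss, so it is not a neutral choice.
- *The bias is built in by assumption.* Selective loss that is equal in number across arms gave 0.248–0.250. That is correct, and no section documents differential loss. It does not remove the concern, because one common rule also gave 0.21–0.22.
- *The comparison favours interim data.* Loss depended on observed growth, so missing-at-random held exactly. This stands, and is the reason for a sensitivity analysis. Estimating the covariance instead of treating it as known did not change the result.
- *A mixed model is not a ready answer.* This stands. Infants enter at about 27 to 32 weeks postmenstrual age, so the time scale must be defined. A model run through to 36 weeks would project growth after death and could override the transfer rule. Multiple imputation with the existing regression would serve as well.

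A reader might also infer that every infant without a 36-week value is lost, or that the plan prescribes a completer analysis against its own intent-to-treat statement. The documents support neither. The value at transfer is a defined endpoint, and section 5.2.2 is silent on missing values. Allowing for drop-out in the sample size is ordinary practice.

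**Conclusion.** The point holds as a gap in section 5.2.2: an intent-to-treat label, a two-point outcome, a model that omits infants without the second value, and no stated alternative. It should be closed, but it does not invalidate the design. Under random loss of 8 of 90 the estimate is unbiased and power stays near 0.80. Under assumed growth-related loss of 8, a true 0.25 is estimated at about 0.19 to 0.23 in most runs, against about 0.25 with the weekly values. The size rests on the assumed mechanism, loss rate and covariance; the documents fix only the 0.25, the 0.4, the 82 and the 90.

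Three stronger inferences are not supported. The documents do not show that this bias will occur. The shift toward no effect belongs to the scenarios simulated, and a different pattern of loss could push the other way. Nor would a repeated-measures model by itself make the analysis intent-to-treat: it relies on missing-at-random, adds almost nothing for an infant with no measurement after 2 weeks, and does not decide how deaths count.

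**What to change.** In section 5.2.2, state that the primary analysis includes all randomised infants by using the weekly Z-scores, and choose one of two routes for each growth measure:

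1. Keep the stratum-adjusted linear regression and multiply impute a missing endpoint from arm, gestational age and the observed weekly Z-scores.
2. Fit a mixed model to the weekly Z-scores with a pre-stated covariance structure, on time since 2 weeks of age, with the window length to 36 weeks postmenstrual age set by gestational age.

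With either route:
- Keep the value at transfer as the endpoint for transferred infants, and say what applies to discharge home before 36 weeks.
- State how deaths enter the estimand, and do not impute or project growth after death.
- Say whether the Week 36 Status form of an early leaver supplies an endpoint.
- Report the complete-case regression as supportive.
- Add one delta-adjusted sensitivity analysis over a pre-stated range. As a guide to scale, if all 8 lost infants were in one arm of 45, shifting their values by 0.25 would move that arm's mean by 0.25 × 8/45 = 0.044.

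The cost is SAP wording, a little more analysis work and a missing-at-random assumption that the sensitivity analysis probes. No new data are needed. The text should be fixed before outcomes are compared by arm.

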5.3 DATA SAFETY AND MONITORING PLAN

A Data Safety and Monitoring Committee (DSMC), headed by [name], Professor of Pediatrics, University of Iowa Carver College of Medicine will monitor the progress of the study when 25%, 50% and 75% of the trial subjects have reached hospital discharge. [name], who has extensive experience with DSMCs, will be responsible for recruiting the necessary individuals with expertise in neonatology, biostatistics, bioethics and clinical trials to establish the DSMC. The DSMC will review accumulated blinded study data to ensure that the intervention is not leading to harm. If there is a significant imbalance of secondary outcome rates between the study arms, the proper course of action will be discussed by the study PIs and the DSMC. The DSMC will not be charged with assessing efficacy before conclusion of the trial; therefore, no loss of alpha will result from the planned interim safety analyses.

Safety outcomes include incidence of mortality up through 36 weeks PMA, BPD, and ROP. The DSMC may request other outcomes at their prerogative. The DSMC will examine other safety outcomes, including all reported deaths and serious adverse events by treatment group in considering a recommendation to suspend the trial for safety reasons.

SECTION 5. REFERENCES

- 1. Fenton, T.R. and J.H. Kim, A systematic review and meta-analysis to revise the Fenton growth chart for preterm infants. BMC Pediatr, 2013. **13**: p. 59.
- 2. Griffin, I.J., et al., *Postnatal growth failure in very low birthweight infants born between 2005 and 2012.* Arch Dis Child Fetal Neonatal Ed, 2016. **101**(1): p. F50-5.
- 3. Horbar, J.D., et al., Weight Growth Velocity and Postnatal Growth Failure in Infants 501 to 1500 Grams: 2000-2013. Pediatrics, 2015. **136**(1): p. e84-92.
- 4. Ehrenkranz, R.A., et al., *Growth in the neonatal intensive care unit influences neurodevelopmental and growth outcomes of extremely low birth weight infants.* Pediatrics, 2006. **117**(4): p. 1253-61.
- 5. Ehrenkranz, R.A., et al., Longitudinal growth of hospitalized very low birth weight infants. Pediatrics, 1999. **104**(2 Pt 1): p. 280-9.
- 6. Franz, A.R., et al., *Intrauterine, early neonatal, and postdischarge growth and neurodevelopmental outcome at 5.4 years in extremely preterm infants after intensive neonatal nutritional support.* Pediatrics, 2009. **123**(1): p. e101-9.

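### Robust Poisson regression is the only method planned for binary secondary outcomes, and it gives a spuriously significant relative risk when exactly one arm has no events; section 5.2.2 needs a zero-event rule.

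*Combined protocol and SAP*

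**What the plan says.** Section 5.2.2 assigns linear regression to continuous secondary outcomes and "robust Poisson regression for binary or categorical outcomes to obtain adjusted relative risk estimates for the treatment effect". It adds that every comparison by treatment "will be adjusted for the stratification variable of gestational age". It names no exact, penalised or other sparse-data method and has no rule for an arm without events.

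Aim 3 (section 2.1) counts severe ROP, meaning stage 3 or higher or treated, among the secondary outcomes, and Hypothesis 3 says the algorithm will not worsen it. Section 3.2.9 lists ROP without a severity cut-off. No expected rate is given for either version.

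Death is not in the secondary outcome list. It appears in section 5.3: "Safety outcomes include incidence of mortality up through 36 weeks PMA, BPD, and ROP". The same section says: "If there is a significant imbalance of secondary outcome rates between the study arms, the proper course of action will be discussed". It names no test for that imbalance.

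**The concern.** Robust Poisson regression is a sound way to estimate a relative risk when both arms have events. It breaks down when one arm has none, and it does so without warning: the software returns an estimate, a small standard error and a minute p-value, not an error message. In a trial of this size an uncommon morbidity could easily fall in one arm only.

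A single case of severe ROP in one arm could then be tabulated as overwhelming evidence of harm or benefit, on an outcome that Hypothesis 3 uses to claim safety. If the analyst notices and changes method, the replacement is chosen after the data have been seen.

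**Working it through.** **Inputs.** Allocation: "randomization will be carried out in REDCap to management arms 1:1" (section 3.2.3). Enrolment: up to 90 (section 5.2.3), so 90/2 = 45 per arm. Safety reviews at 25%, 50% and 75% (section 5.3): about 11, 22 and 34 per arm. Event rates for severe ROP are not given, so 2%, 5% and 10% are assumptions.

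**The plan's own figure.** Section 5.2.3 seeks power for "identifying a difference in weight Z-score of 0.25 at 36 weeks postmenstrual age". Its other inputs are a standard deviation of 0.4, a 5% significance level and 80% power. Two-sided, n = 2 × (1.960 + 0.842)² × 0.4² / 0.25² = 40.2, rounded up to 41 per arm. This agrees with the stated "total sample size of 82 patients (41 per group". It concerns weight only; no binary outcome was used to size the trial.

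**Why the standard error does not grow.** Take k events among n infants in one arm and none in the other, without covariates. The robust variance of the log relative risk is the sum of one term per arm.

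- Arm with events: 1/k − 1/n.
- Empty arm: its fitted mean m shrinks towards zero, and its term is n·m²/(n·m)² = 1/n however small m becomes.
- Sum: 1/k. The standard error is therefore 1/√k, while the log relative risk drifts without limit and stops where the iterations stop.

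**Fits at 45 per arm** (Poisson model, log link, arm plus gestational-age stratum, robust standard error):

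| Events | Log RR (absolute) | Robust SE | Wald p | Fisher p |
|---|---|---|---|---|
| 1 vs 0 | 20.4 | 1.00 | about 4e-92 | 1.00 |
| 2 vs 0 | 20.4 | 0.71 | about 9e-183 | 0.49 |
| 3 vs 0 | 21.3 | 0.58 | about 9e-299 | 0.24 |
| 4 vs 0 | 21.4 | 0.50 | printed as 0 | 0.117 |
| 5 vs 0 | 21.4 | 0.45 | printed as 0 | 0.056 |
| 6 vs 0 | 22.4 | 0.41 | printed as 0 | 0.026 |

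The pattern is the same at 41 per arm and without the stratum term. The model-based standard error gives p of about 0.999 on the same data, so the robust variance combined with the Wald test is the cause. The interval is no better: for 2 vs 0, 20.4 ± 1.96 × 0.71 gives a log relative risk from 19.0 to 21.8.

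**How often, with no treatment effect.** With true risk p in both arms and q = (1 − p)^n, the chance that exactly one arm is empty is 2q(1 − q). At n = 45:

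- p = 2%: q = 0.403; 2 × 0.403 × 0.597 = 48%.
- p = 5%: q = 0.099; 2 × 0.099 × 0.901 = 18%.
- p = 10%: q = 0.0087; 2 × 0.0087 × 0.9913 = 1.7%.

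At 41 per arm the figures are 49%, 21% and 2.6%.

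**Simulation** (3,000 null trials per setting, 45 per arm, nominal 5% level):

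| Assumed risk | Robust Poisson throughout | Fisher's test when an arm is empty |
|---|---|---|
| 2% | 48.3% | 0.1% |
| 5% | 18.7% | 0.6% |
| 10% | 3.5% | 2.0% |

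At 2% and 5% virtually all the excess comes from samples with one empty arm. When both arms had at least one event, robust Poisson rejected in 0 to about 1.4% of null trials.

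**The case against.** Several points can fairly be made against this.

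- *The plan asks for relative risks, not p-values, and a value near e^20 beside 1 vs 0 is obviously meaningless.* A careful analyst would probably notice. But the estimate and its interval are as wrong as the p-value, and the plan offers nothing to put in their place. This lowers the severity; it does not remove the gap.
- *The fault is the Wald test, not the Poisson model.* True. An unadjusted likelihood-ratio statistic for k vs 0 with equal arms is 2k·ln 2, or 1.39 (p = 0.24) for 1 vs 0. No such test is named, and the Wald test is the usual output of robust Poisson.
- *Many outcomes are common.* This stands. Section 2.2 reports 60% and 48% of the two earlier cohorts on supplemental oxygen at 36 weeks. At 48%, the chance of exactly one empty arm is about 0.15% even at 11 per arm. Oxygen need is not exposed, nor is bronchopulmonary dysplasia if it is defined by oxygen at 36 weeks (an assumption).
- *Rarity alone is not the fault.* This also stands: with at least one event in each arm the method was conservative.

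A reader might infer that the safety committee will be misled, since section 5.3 speaks of a significant imbalance. The documents do not support that. They name no test for the reviews, the wording may mean a clinically notable imbalance, and the consequence is discussion, with biostatistical expertise on the committee. If robust Poisson were used there, the chance of exactly one empty arm at assumed risks of 2%, 5% and 10% would be 32%, 49% and 43% at 11 per arm; 46%, 44% and 18% at 22; and 50%, 29% and 5% at 34. Those figures are conditional. Likewise, applying the method to death is an inference, because death is a safety outcome and not a listed secondary outcome.

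**Conclusion.** The concern holds for binary secondary outcomes in which exactly one arm has no events; severe ROP at the final analysis is the clearest case. For 1 to 5 vs 0 at 45 per arm the significance itself is spurious. From 6 vs 0 Fisher's test is also significant, so only the size of the estimate, interval and p-value is wrong. If both arms are empty the model cannot be fitted and there is no false signal.

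The size depends on the assumed event rate: about 48%, 18% and 2% of null trials at 2%, 5% and 10% risk. At about 10% or more the problem largely disappears at full enrolment. The calculation assumes equal true risk in the arms, 45 analysed per arm and a Wald test with a robust standard error.

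The primary analysis is linear regression and is untouched. This is a gap that should be closed before analysis, not a flaw that invalidates the trial.

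**What to change.** Add to section 5.2.2:

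*If either arm has zero events for a binary outcome, no relative risk or Wald p-value from robust Poisson regression is reported. The arms are compared with an exact test stratified by gestational-age stratum, and a stratified risk difference with a score (Miettinen-Nurminen) interval is reported. The same rule applies if robust Poisson regression is used for safety outcomes at DSMC reviews.*

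The cost is two or three sentences, with no extra data or patients. The affected outcomes are reported as risk differences instead of relative risks, and the exact test is conservative.

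The rule should stop at empty arms. Nothing computed here supports a higher threshold such as fewer than five events. Exact testing of every binary outcome at each safety review would weaken the detection of harm: for an assumed 48% vs 75%, power falls from about 44% (unadjusted robust Poisson) to 33% (Fisher) at 22 per arm, and from 62% to 56% at 34 per arm.
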